- Duration of TEAEs experienced by ≥5% of All Subjects by Preferred Term

• Incidence of TEAEs experienced by ≥5% of All Subjects by Preferred Term and Exposure Interval

A subject having the same AE (as determined by the coded MedDRA preferred term) more than once will be counted only once in the calculation of the number and percentage of subjects for that AE. Similarly, if a subject has more than one AE in a System Organ Class, the subject will be counted only once in the number of subjects with an AE for that System Organ Class. If a subject has the same AE on multiple occasions, the highest severity (severe > moderate > mild) recorded for the event will be presented in the AE by severity summary. Similarly, if a subject has the same AE on multiple occasions, the closest relationship (related > not related, where related includes definitely related, probably related, and possibly related; and not related includes probably not related and definitely not related) recorded for the event will be presented in the AE by relationship summary. If a subject has the same AE on multiple occasions, the first presentation will be used in the incidence table and the longest duration will be used in the duration table.

The number and percentage of subjects with TEAE during the ALK5461-208 study will be summarized by System Organ Class, Preferred Term, and duration of exposure since the first dose of the study drug in the ALK5461-208 study (1 day to <1 month, \geq 1 to <3 months, \geq 3 to <6 months, \geq 6 to <9 months, \geq 9 to <12 months, and \geq 12 months). For each exposure interval, the percentage will be calculated as the number of subjects with a new TEAE that started during the exposure interval, relative to the number of subjects exposed during the interval. Separate tables for prior ALKS 5461 exposure and overall will be provided.

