Descriptive statistics (number of subjects, mean, SD, median, 10th percentile, 90th percentile, minimum, and maximum) of duration (days) of TEAEs experienced by ≥5% of All Subjects will be provided by Preferred Term during treatment period for the Safety Population. The duration is defined as number of days from the TEAE start date to the TEAE stop date during the ALK5461-208 study, inclusive. If a TEAE is ongoing at the end of the treatment period, the TEAE stop date is imputed by last dose date plus 1 day. For those subjects who have the same event (same PT term) that is treatment emergent on multiple occasions, we will choose the longest duration as stated above. For partial TEAE start or stop date:

- If only day is missing but month available, TEAE start date will be imputed as the first day of the month and TEAE stop date will be imputed as the last day of the month.
- If both month and day are missing, TEAE start date will be imputed as the Visit 2 date or January 1st whenever applicable, and TEAE stop date will be imputed as the last dose date or December 31st whenever applicable.

The Incidence (%) of TEAEs experienced by $\geq 5\%$ of All Subjects by Preferred Term and Exposure Interval (1 day to <1 month, ≥ 1 to <3 months, ≥ 3 to <6 months, ≥ 6 to <9 months, ≥ 9 to <12 months, and ≥ 12 months) will be presented by prior ALKS 5461 exposure and overall during treatment period for the Safety Population. For those subjects who have the same event (same PT term) that is treatment emergent on multiple occasions, the first instance where that event was treatment emergent will be used, as stated above. The incidence (%) is calculated by n/m x 100%, where n is defined as the number of subjects with newly emergent or worsened adverse events during the exposure interval; m is defined as the number of subjects who had

treatment exposure during the exposure interval. The incidence (%) of TEAE over time will also be presented graphically. For each preferred term, a bar graph will be presented by prior ALKS 5461 exposure and overall. The number of n/m of three groups will be listed below the figure.

Subgroup analyses are planned for TEAEs only. Subgroups to include:

- Demographics (age [<55 years, ≥55 years], race [white, all other races], gender [female, male])
- Region (US, non-US)
- ADT class (SSRI, SNRI, and other)
- Benzodiazepines use (yes, no)
- Opioid use (yes, no)

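### In the TEAE incidence-by-exposure-interval table and bar graphs (SAP 3.7.2), subjects who have already had the event stay in the denominator but can no longer enter the numerator, so incidence after the first interval is understated

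*SAP*

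**What the plan says.** SAP 3.7.2 defines the table for common terms and the matching bar graphs as follows.

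- Formula: "The incidence (%) is calculated by n/m x 100" percent.
- Numerator: "n is defined as the number of subjects with newly emergent or worsened adverse events during the exposure interval". This is limited by the rule for a preferred term that is treatment emergent more than once in the same subject: "the first instance where that event was treatment emergent will be used". The general counting paragraph agrees: "the first presentation will be used in the incidence table and the longest duration will be used in the duration table".
- Denominator: "m is defined as the number of subjects who had" treatment exposure in the interval. Nothing removes subjects with an earlier occurrence.
- Intervals: six, namely under 1 month, 1 to under 3, 3 to under 6, 6 to under 9, 9 to under 12, and 12 months or more.
- Display: by prior ALKS 5461 exposure and overall, with n/m listed below each figure.

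The same section plans companion tables of TEAEs by duration of exposure, one by SOC and preferred term and one by preferred term in decreasing frequency. Their percentage is the number of subjects with a new TEAE starting in the interval, "relative to the number of subjects exposed during the interval".

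**The concern.** The numerator and denominator describe different sets of people. A subject with nausea in month 1 cannot be counted for nausea in any later interval, yet is in the denominator of every later interval with exposure. The numerator's wording on worsened events does not bring that subject back, because the first-instance rule addresses exactly the case of a term that is treatment emergent on several occasions. Recurrences would otherwise qualify, since SAP 3.7.2 benchmarks severity against the period before baseline and not against earlier on-treatment events.

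The first interval is unaffected and every later one is pulled down, so the error runs one way, towards an apparent decline. That matters because the objective is long-term safety (Protocol section 6) and only short-term data existed beforehand (Protocol 5.1). A reader will look to these bars to see whether common events keep arising late. If the bars are read instead as any occurrence in the interval, they are still too low, because recurrences are dropped.

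**Working it through.** The plan states no incidence figure, so there is nothing to reproduce. The check is algebra on the SAP's definitions, followed by illustrations.

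**Identity.** For one preferred term and one interval, let m be subjects exposed, p those in m whose first occurrence fell in an earlier interval, and n first occurrences in this interval.

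- Planned figure: n/m.
- First-occurrence risk among those still at risk: n/(m − p).
- Ratio: (n/m) ÷ (n/(m − p)) = (m − p)/m = 1 − f, where f = p/m.

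The shortfall is relative. With m = 1,000 and an assumed at-risk incidence of 4%, f = 5%, 10% and 20% give 4% × 0.95 = 3.80%, 4% × 0.90 = 3.60% and 4% × 0.80 = 3.20%. At f = 20% the gap is 0.8 percentage points.

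**Size under constant hazard.** Assumptions: no dropout, nominal months, and P = share of subjects with the event by 12 months. Then the true risk in any 3-month interval is 1 − (1 − P)^(3/12), f at month t is 1 − (1 − P)^(t/12), and the planned figure is true risk × (1 − f).

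For P = 25%, the true risk is 1 − 0.75^0.25 = 6.94% in each 3-month interval:

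| Interval (months) | f | Planned n/m | True at-risk |
|---|---|---|---|
| 3 to <6 | 6.9% | 6.46% | 6.94% |
| 6 to <9 | 13.4% | 6.01% | 6.94% |
| 9 to <12 | 19.4% | 5.59% | 6.94% |

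These three intervals have equal width, so width does not explain the fall.

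Other values of P, months 9 to <12:

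| P | f | Planned n/m | True at-risk |
|---|---|---|---|
| 5% | 3.8% | 1.23% | 1.27% |
| 10% | 7.6% | 2.40% | 2.60% |
| 40% | 31.8% | 8.17% | 11.99% |

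**Early-onset term.** If P = 25% and 80% of cases start in month 1 (assumed), f at month 9 is 23.7%, and months 9 to <12 read 1.33% against 1.74%.

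**Dropout.** The share f is taken among subjects still exposed. If 25% have had the event, and 50% of them but only 10% of the others then leave (assumed), f = (0.25 × 0.5) ÷ (0.25 × 0.5 + 0.75 × 0.9) = 0.125 ÷ 0.80 = 15.6%, against 25% if both leave at the same rate.

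**Exposure groups.** SAP 3.1 generally summarises only data collected in study 208, and TEAEs are counted from Visit 2. Prior-exposed subjects may have had early events in the antecedent study, where they do not count towards f. The two groups can therefore have different f, and a different understatement, in the same interval. The documents give no basis for putting a number on this.

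**The case against.** Several points on the other side have weight.

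- **It is a defined quantity.** The share of subjects exposed in an interval whose first onset falls in it is clearly specified. That is true, but the SAP labels it incidence and plots it over time, and a reader will take it as risk.
- **It is partly recoverable.** Because n/m is printed and each subject counts once per term, the sum of earlier n's is an upper bound on p. The at-risk value therefore lies between n/m and n/(m − sum of earlier n's). This only brackets it, and the bracket widens as earlier cases leave treatment.
- **Other outputs bear on timing.** There are the companion tables, the AE listings and Kaplan-Meier time to discontinuation due to AE (SAP 3.2.2). These stand, so the affected table is not the only view of late events, and it covers only terms at or above 5%. None of them gives an at-risk incidence over time.
- **The companion tables may be sound.** A reader might infer that they share the flaw, since they use the same all-exposed denominator. The text does not establish that. The rule that "the first presentation will be used in the incidence table" refers to a single table, and once-only counting could mean once per cell. Their rule is unsettled, not shown to be wrong.
- **The display is descriptive.** No test depends on it, which limits the consequence.

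**Conclusion.** The defect stands for the table and bar graphs of common TEAEs by exposure interval. It follows from the SAP's own definitions: after the first interval the printed figure is the at-risk first-occurrence incidence multiplied by 1 − f. The size depends on assumed rates, onset pattern and dropout. It is material for common or early-onset terms, modest at 10% 12-month incidence and negligible near 5%. It is smaller if subjects with the event leave more often.

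Two stronger readings are not supported. A reader might picture four equal bars at a constant 10% risk per three months falling from 10.0 to 7.3%, a 27% relative drop. The SAP has six unequal intervals. Under that hazard the first five bars would read about 3.5, 6.5, 9.0, 8.1 and 7.3%, rising first because the early intervals are shorter. Across the three equal-width bars the fall is (9.0 − 7.3)/9.0, about 19%, and 10% per quarter already implies 1 − 0.9^4 = 34% with the event by 12 months. A reader might also infer a known distortion between the exposure groups. The documents support only that the understatement may differ if the shares with earlier events within study 208 differ.

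**What to change.** In SAP 3.7.2 adopt one of two rules for this table and its graphs.

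1. For each preferred term and interval, define m as subjects exposed in that interval with no earlier treatment-emergent occurrence of that term in study 208. This gives first-occurrence risk.
2. Keep m as all exposed subjects and count in n every subject with a new or worsened onset in the interval, whatever happened before. Label it as any onset in the interval.

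The two rules answer different questions, so the choice should be footnoted on the table and figures. For the companion duration-of-exposure tables, state whether a subject with an earlier occurrence can be counted again in a later interval, and match the denominator to that choice.

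The cost is SAP wording and programming, with no new data. Under the first rule m varies by term and must be printed per row in the table; the figures already list n/m for each term.

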At Visit 2, all eligible, consenting subjects will begin the treatment period. Subjects entering the study already receiving ALKS 5461 will not require titration; all other subjects will require a 1-week ALKS 5461 titration period. Depending on the antecedent study, the titration may be blinded per blinding schemes as described in the protocol. From Week 2 to 52, all participating subjects will take ALKS 5461 2/2 and an approved ADT, with allowable ALKS 5461 dose adjustments for tolerability as described in the protocol.

During the 52-week treatment period, subjects will return to the clinic for periodic scheduled visits (Visits 2-14) at which safety, tolerability, and treatment effect over time will be assessed.

A 4-week safety follow-up period will occur following the ALKS 5461 treatment period. During the 4-week follow-up period, there are a total of 4 clinic visits (Visits 15-18), as well as 7 safety assessments by phone. Please refer to the protocol for a detailed schedule of assessments. A brief schematic of study design is provided in Figure 1. A summary of the schedule of safety assessments is presented in Table 1.

Figure 1: Study Design Schematic

Abbreviations: EOS=end of study; EOT=end of treatment; ET=early termination; PLI=prospective lead-in; V=visit

Table 1: Schedule of Safety Assessments

Study Number	Dosing Schedule (Days)	Vital Signs ^a	Clinical Laboratory Testing ^b	12-Lead ECG	C-SSRS ^d	COWS ^e	AEs
ALK5461- 208	Treatment: 1-365 (1 year) Titration: 1-7 (1 week) Safety Follow Up: 366- 393 (1 month)	Screening, Days 1°, 8, 15, 29, 43, 57, 99, 141, 183, 225, 267, 309, 365, 366, 372, 379, 393	Screening, Days 1°, 8, 99, 183, 267, 365, 393	Screening, Days 1°, 8, 183, 365, 393	Screening, Days 1°, 8, 15, 29, 43, 57, 99, 141, 183, 225, 267, 309, 365, 366, 372, 379, 393	Days 365, 366, 372, 379, 393 ^e	Throughout

Abbreviations: ECG=electrocardiogram; C-SSRS=Columbia-Suicide Severity Rating Scale; COWS=Clinical Opiate Withdrawal Scale; AEs=Adverse Events

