3.5. Treatment Adherence Rate and Extent of Exposure

Treatment adherence to the daily dosing schedule of study drug is measured as the rate of actual compared to intended number of doses to be taken during the ALK5461-208 study. Percentage of treatment adherence will be calculated during 52-week treatment period for the Safety Population as follows:

 $\frac{\text{Total tablets taken}}{\text{Total tablets subject should have taken from the first dose date to the last dose date, inclusive}}$

Duration of exposure to study drug is defined as the number of days from the first dose date of study drug taken to the date of the last dose taken during the ALK5461-208 study, inclusive.

Treatment adherence and exposure of study drug will be summarized by prior ALKS 5461 exposure and overall for the Safety Population.

Treatment adherence will be summarized as a continuous measure using descriptive statistics (number of subjects, mean, SD, median, minimum, and maximum) and as a categorical measure using the number and percentage of subjects in each adherence rate category (rounded to the whole number): <70%; $\ge70\%$ to 80%; >80% to 90%; >90% to 100%; >100% to 110%; >110% to 119%; and $\ge120\%$.

The number of subjects exposed to study drug and the average days of treatment will be summarized as a continuous measure using descriptive statistics (number of subjects, mean, SD, median, minimum, and maximum).

The exposure to ADT will be summarized by ADT class (SSRI, SNRI, TCA, MAOI and other) and Preferred Term (ADT name) using descriptive statistics in a similar fashion. In addition, descriptive statistics of mean daily dose of ADT will be summarized by ADT class and Preferred Term.

The descending cumulative exposure of study drug will be categorized as ≥ 1 day, ≥ 1 month, ≥ 3 months, ≥ 6 months, ≥ 9 months and ≥ 12 months, and will be summarized as a categorical measure using the number and percentage of subjects in each category.

The definitions in Table 3 will be used to define cumulative exposure.

Table 3: Definitions to Define Study Drug Cumulative Exposure

	Definition	Programming Derivation
≥ 1 day	≥ 1 day	
≥ 1 month	≥ 23 days (3 weeks)	\geq (365.25/12)-7 days
\geq 3 months	\geq 84 days (12 weeks)	\geq [(365.25/12)x3]-7 days
≥ 6 months	≥ 169 days (24 weeks)	\geq [(365.25/12)x6]-14 days
≥ 9 months	≥ 260 days (37 weeks)	\geq [(365.25/12)x9]-14 days
≥ 12 months	≥ 351 days (50 weeks)	≥ 365.25 -14 days

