3.7.2. Adverse Events

Adverse events will be coded by System Organ Class and Preferred Term using the Medical Dictionary for Regulatory Activities MedDRA version 19.0. The verbatim term will be included in the AE listings. An AE will be considered as a treatment emergent adverse event (TEAE) if it starts or worsens (if present at baseline) on or after the baseline during treatment period. An AE will be considered as a PDEAE if it starts or worsens during the Post-discontinuation Safety Period which is after the last dose date plus 1 day. For the determination of TEAEs during the treatment period, AEs with the greatest severity before the baseline will be used as the benchmark for the comparison of the AEs occurring during the treatment period. For PDEAEs, the greatest severity before or on the last dose date plus 1 day will be used as the benchmark for the comparison of the AEs occurring during the Post-discontinuation Safety Period.

All AEs will be listed by subject. TEAEs / PDEAEs, deaths, serious adverse events (SAEs), AEs leading to study discontinuation will be included in the summary tables. Summary tables will be provided by prior ALKS 5461 exposure and overall for the Safety Population. For AEs leading to study discontinuation or deaths, the AEs will be summarized in the period in which the discontinuation or death occurred. Drug related TEAEs include those scored as definitely related, probably related, and possibly related by the investigator.

The following summary tables will be produced for the treatment period / Post-discontinuation Safety Period by prior ALKS 5461 exposure and overall for the Safety Population:

- Overview AE summary tables (TEAEs / PDEAEs)
- TEAEs / PDEAEs by System Organ Class and Preferred Term
- TEAEs / PDEAEs by Preferred Term in decreasing frequency
- TEAEs / PDEAEs experienced by ≥5% of subjects (in any group) by Preferred Term
- TEAEs / PDEAEs by System Organ Class, Preferred Term, and Severity
- Drug-related TEAEs by System Organ Class and Preferred Term
- SAEs (fatal and non-fatal) by System Organ Class and Preferred Term
- SAEs (fatal and non-fatal) by Preferred Term in decreasing frequency
- AEs leading to study discontinuation by System Organ Class and Preferred Term
- AEs leading to study discontinuation by Preferred Term in decreasing frequency
- TEAEs by System Organ Class, Preferred Term, and Duration of Exposure
- TEAEs by Preferred Term in decreasing frequency and Duration of Exposure

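### TEAE incidence over time is plotted as a crude proportion in exposure intervals of unequal length, with no person-time rate, so bar height partly reflects interval width

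*SAP*

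**What the plan says.** SAP 3.7.2 plans TEAE tables by duration of exposure, including "TEAEs by Preferred Term in decreasing frequency and Duration of Exposure", and an incidence table with bar graphs for preferred terms reported by at least 5% of all subjects. All use the same six intervals: 1 day to <1 month, 1 to <3, 3 to <6, 6 to <9, 9 to <12, and ≥12 months.

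- **Duration-of-exposure tables.** The percentage is subjects with a new TEAE starting in the interval, "relative to the number of subjects exposed during the interval".
- **Incidence table and graph.** The incidence is n/m × 100%. n counts subjects with a newly emergent or worsened event in the interval. "m is defined as the number of subjects who had" treatment exposure in it. Only a subject's first treatment-emergent instance of a term counts.
- **Display.** "The incidence (%) of TEAE over time will also be presented graphically", and "The number of n/m of three groups will be listed below the figure".

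SAP 3.5 converts the same month labels to days: "The definitions in Table 3 will be used to define cumulative exposure". There, 12 months means "≥ 351 days (50 weeks"). SAP 3.7.2 does not say whether those limits apply to the TEAE intervals. SAP Table 1 gives the dosing schedule as "Treatment: 1-365 (1 year"), and SAP Table 2 ends the AE treatment period one day after the last dose.

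Neither document plans a person-time TEAE rate or a time-to-first-TEAE analysis. Kaplan-Meier methods are planned only for treatment discontinuation (SAP 3.2.2).

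**The concern.** A proportion accumulates with time at risk, so a three-month interval collects more first events than a one-month interval at the same underlying rate. A chart labelled as incidence over time invites a comparison of heights across intervals. Read that way, a constant risk seems to climb until months 3–6, a moderate early excess is blunted or reversed, and risk seems to collapse at ≥12 months because hardly any treatment time falls there.

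Long-term safety and tolerability is the study's only objective. Whether events cluster early or emerge later is a natural question for the reader of the report, and this display could suggest the wrong answer.

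**Working it through.** **Interval lengths.** The plan's own day limits reproduce. With a month of 365.25/12 = 30.44 days, subtracting 7 days (1 and 3 months) or 14 days (6, 9 and 12 months) gives 23.4, 84.3, 168.6, 259.9 and 351.3. These round to the 23, 84, 169, 260 and 351 of SAP Table 3.

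- Table 3 limits, dosing days 1–364: L = 22, 61, 85, 91, 91, 14 days.
- Calendar months: L = 30.4, 60.9, 91.3, 91.3, 91.3 days and a remnant taken as 3 days (treatment to Day 365, Visit 14 ±3 days, AEs to last dose + 1 day).

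**Assumptions.** The documents give no event or dropout rates. I take a 5–20% annual risk for a preferred term, first with no dropout.

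**Constant risk.** Daily hazard h = −ln(1 − annual risk)/364. With s the days from first dose to the start of the interval, bar = exp(−h·s) × (1 − exp(−h·L)). At 10%, h = 0.10536/364 = 0.0002895, a true rate of 0.88 per 100 patient-months throughout.

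**Two-fold early excess.** The hazard is 2h in the first interval and h afterwards, with total hazard held at 0.10536. Under Table 3 limits, h = 0.10536/(364 + 22) = 0.0002730, so the first bar is 1 − exp(−2 × 0.0002730 × 22) = 1.19%. The true rates are 1.66 then 0.83 per 100 patient-months. Under calendar months (368.25 days in all) they are 1.61 then 0.80.

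Bars in %, 10% total risk, no dropout:

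| Scenario | <1 | 1–<3 | 3–<6 | 6–<9 | 9–<12 | ≥12 |
|---|---|---|---|---|---|---|
| Constant, Table 3 | 0.63 | 1.74 | 2.37 | 2.48 | 2.41 | 0.37 |
| Constant, calendar | 0.88 | 1.73 | 2.54 | 2.47 | 2.41 | 0.08 |
| Two-fold early, Table 3 | 1.19 | 1.63 | 2.23 | 2.33 | 2.27 | 0.34 |
| Two-fold early, calendar | 1.60 | 1.57 | 2.31 | 2.25 | 2.20 | 0.07 |

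**Ratio of the 6–9 month bar to the first, constant risk of 5, 10 and 20%.** Table 3: 4.0, 3.9, 3.65. Calendar: 2.9, 2.8, 2.6.

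**Early excess needed for the two bars to be level, 5–20% total risk.** About 3.7–4.0 times the later rate (Table 3) or 2.6–2.9 times (calendar). Larger excesses show, but shrunken.

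**Dropout and commoner events.** With constant dropout hazard d, bar = exp(−h·s) × h/(h + d) × (1 − exp(−(h + d)·L)).

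- 50% one-year dropout (d = ln 2/364), 10% risk, calendar: 2.27/0.85 = 2.7. At 20% risk the ratio is 2.49.
- 30% risk, no dropout, calendar: 2.44.
- Worst case, reading the minimum exposure targets as retention (300/1500 = 20% at 6 months, 100/1500 = 6.7% at 12): calendar ratio 2.55 at 5% risk and 2.14 at 30%.
- Two-fold early excess in that worst case, calendar: 1.27 at 5% risk, 1.06 at 30%, and 0.96 in a stress case of 40%.

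**Depletion.** In the incidence table and graph, subjects who already had the event stay in m but cannot enter n again. At 10% constant risk the 9–12 month bar is therefore 1 − exp(−0.0002895 × 259) = 7% too low. The first-instance rule is not explicit for the duration-of-exposure tables.

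**Check of the remedy.** First events per event-free person-time give a ratio of 6–9 months to first interval of 1.00 under constant risk and 0.50 under a two-fold early excess. In simulation (10% constant risk; 0, 30 and 50% dropout) the rate was 0.84–0.89 per 100 patient-months in every interval under both sets of limits.

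**The case against.** The quantity is a valid interval proportion, clearly defined. Interval labels are in months and n/m is printed under the figure, so a reader can see that the first interval is shorter and can rescale roughly. No test or decision depends on it. Because m is recounted in each interval, loss between intervals is already handled. The graphs are drawn by prior-exposure group, and comparing groups within an interval is sound. The day limits may appear in the separate programming specifications or mock displays, which are not available here.

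Most of this stands, and it makes the point one of presentation. It does not remove the width effect: recounting m does nothing about interval length, and n/m carries no exposure days, so the rate cannot be recovered exactly.

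A reader might go further and infer that the SAP built these displays to compare early with later risk. It states no such purpose. Nor does the depletion effect extend with certainty to every by-interval table.

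**Conclusion.** The point holds as a cheap improvement to a descriptive display. Under constant risk of 5–20% a year without dropout, the 6–9 month bar is 3.65–4.0 times the first if the Table 3 limits apply, or 2.6–2.9 times with calendar months. Heavier dropout or commoner events bring the calendar figure to about 2–2.5. All event and dropout rates are assumptions.

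It is tempting to say that 2.6–4.0 holds whenever risk is constant, or that a two-fold early excess is always hidden. Neither is supported. The range needs low dropout and risk of 20% or less. The reversal is robust at 5–20% risk, but the bars come close to level at about 30% risk, or cross beyond it, under the dropout implied by the minimum exposure targets.

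Nor does this undermine the safety evaluation as a whole. The 3–6, 6–9 and 9–12 month bars are nearly equal in width (85, 91 and 91 days, or 91.3 each) and can be compared. Within-interval group comparisons, the overall TEAE, SAE and AESI tables, and the Kaplan-Meier display of discontinuation are unaffected. What misleads is the early-versus-later contrast and the fall at ≥12 months.

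**What to change.** In the by-interval summaries of SAP 3.7.2, add first events per person-time at risk, for example per 100 patient-months with a 95% CI. Remove a subject from the risk set after the first event of that term or after last dose + 1 day. Plot that rate and keep n/m beneath the figure as planned. State in 3.7.2 which day limits define the intervals, by cross-reference to Table 3 if those are meant.

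Merging ≥12 months into ≥9 months is optional, since it would break alignment with the Table 3 categories. If the interval is kept, add a note on how little time it covers.

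The cost is SAP wording and programming on dates already collected, plus a scale less familiar to readers than percentages.
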